- Grade 3 solicited or unsolicited adverse event that is ongoing, whether or not it is improved or resolving. An unresolved or continuing Grade 1 or Grade 2 adverse event is permissible following the documented determination by the site principal investigator or appropriate sub-investigator, that it would not render study vaccination unsafe or interfere with the evaluation of adverse events or immunologic response.
- Grade 3 solicited or unsolicited adverse event that occurs in the 7 days following study vaccination, lasts for more than 24 hours without decreasing to a Grade 1 or Grade 2, and does not have an alternative etiology.
- Any laryngospasm, bronchospasm, or anaphylaxis within 1 day after administration of study product that is considered related to study product.
- Any generalized urticaria within 3 days after administration of study product that is considered related to study product.
- Serious adverse event related to the study vaccination.
- As deemed necessary by the site principal investigator or appropriate sub-investigator for noncompliance or other reasons.
- Subject refusal of further study vaccination.

- Termination of this trial.
- New information becomes available that makes further administration of the study vaccine unsafe.

Subjects who receive the first study vaccine but not the second vaccination will be encouraged to remain in this trial for follow-up, safety and immunogenicity assessments per [Appendix A: Schedule of Study Procedures and Evaluations](#). If the scheduled visit does not include collection of blood for safety or immunogenicity, the visit may be conducted by phone call/ electronic communication (e.g., email, text message) rather than in person continuing through approximately 6 months after the first study vaccination. See the protocol-specific Manual of Procedures (MOP) for alternate follow-up requirements.

Every attempt will be made to follow all adverse events, including solicited local site and systemic AEs, unsolicited non-serious adverse events, SAEs and MAAEs ongoing at the time of early withdrawal through resolution as per applicable collection times defined for the specific type of adverse event.

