7.3.2. Follow-up Vaccination Visit

Day 8 +2 (post first vaccination), Visit 06

All subjects will return for vaccination on D8. The following assessments will occur.

- Eligibility criteria will be reviewed with subjects prior to study vaccination to ensure continued eligibility (see [Section 5.3](#)).
- Interim medical history will be obtained by interview of subjects to ensure continued eligibility. Any changes since the previous clinic visit or contact will be noted at each clinic visit.
- All concomitant medications (including solicitation for receipt of any non-study vaccines) will be recorded on the appropriate data collection form at each clinic visit. Any new concomitant medications taken since the last clinic visit or phone contact will be reviewed with subjects and assessed for continued eligibility.

- Vital signs, including oral temperature, pulse, and blood pressure, will be obtained to ensure continued eligibility. Subjects must not eat or drink anything hot or cold, or smoke within 10 minutes prior to taking oral temperature.
- A targeted physical examination may be performed prior to study vaccination, if indicated based on review of complete medical history and any updates obtained by interview of subjects since the screening visit, by a study clinician listed on the Form FDA 1572.
- A urine pregnancy test will be performed within 24 hours prior to study vaccination on all females of childbearing potential. Results must be negative and known prior to randomization and study vaccination.
- Venous blood will be collected prior to the study vaccination for safety labs (See [Section 8.2.1](#)).
- Venous blood will be collected prior to the study vaccination for future use assays.
- Venous blood will be collected prior to the study vaccination for immunogenicity and exploratory assays (please refer to [Appendix A](#): Schedule of Study Procedures and Evaluations for type of assays requiring collection).

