- Pre-administration reactogenicity assessments will be performed prior to study vaccination to establish a baseline. Subjects will then receive study vaccine or placebo via intramuscular injection into the opposite arm that was used for the first injection (left or right deltoid). The time of administration will be recorded on the appropriate data collection form. Subjects will be observed for at least 30 minutes after study vaccination. Post-administration reactogenicity assessments will be performed. Any AEs, SAEs, and MAAEs will be recorded on the appropriate data collection form prior to discharge from the clinic.
- Subjects will be provided with a memory aid and other study-related materials to record daily oral temperature, solicited site and systemic AEs, unsolicited AEs, and concomitant medications. Subjects will be encouraged to take their oral temperature around the same time each day. Subjects must not eat or drink anything hot or cold, or smoke within 10 minutes prior to taking oral temperature. Subjects will be instructed on how to use their memory aid and how to measure and record AEs prior to discharge from the clinic. Subjects will be instructed to notify the study center if they develop any severe reactions after study vaccination. If the site principal investigator or appropriate sub-investigator deems the reaction severe enough, further instructions will be given to the subject on the proper course of action, including a return to the clinic for immediate evaluation if appropriate.
- All AEs, SAEs, and MAAEs will be collected and recorded on the appropriate data collection form at each clinic visit.

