On Day 1 and all vaccination visits, vital signs (oral temperature, pulse, and blood pressure) will be collected prior to study vaccination. A urine pregnancy test will be performed within 24 hours prior to study vaccination on all females of childbearing potential. Pre-administration reactogenicity assessments will be performed prior to each study vaccination to establish baseline, then the study vaccination will be given. Subjects will be observed in the clinic for at least 30 minutes after each study vaccination. The study vaccination site will be examined, post-administration reactogenicity assessments will be performed and any AE, SAEs and MAAEs will be recorded on the appropriate data collection form prior to discharge from the clinic. All subjects will receive and complete a subject memory aid from the time of study vaccination through 7 days after study vaccination. Subject memory aids will be reviewed with the subjects for adverse events, (solicited local and systemic AEs and unsolicited AEs) approximately at day 8 after each vaccination.

Reactogenicity assessments will include an assessment of solicited adverse events occurring from the time of study vaccination through 7 days after study vaccination. These include local reactions such as pain, tenderness, erythema (redness), induration (hardness/swelling), pruritic (itching) and bruising as well as systemic AEs such as fever, feverishness (chills, shivering, sweating), fatigue (tiredness), malaise (general unwell feeling), myalgia (body aches/muscular pain), nausea, loss of appetite and headache.

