9.3. Adverse Events

9.3.1. Solicited Events and Symptoms

Solicited adverse events collected 30 minutes post-vaccination (in-clinic assessment) and then daily for 7 days after each vaccination (through Day 8) will be graded on a scale of 0 (absent), 1 (mild), 2 (moderate) and 3 (severe). Local reactogenicity grading are provided in [Table 4](#) and [Table 5](#) and include:

- Pain – experienced without touching the injection site (spontaneous discomfort)
- Tenderness – hurts only when injection site is touched, or the arm is moved
- Erythema (Redness)
- Induration (Hardness/Swelling)
- Ecchymosis (Bruising)
- Pruritus (Itching)

The systemic reactogenicity grading is provided in [Table 6](#) and [Table 7](#) and includes:

- Feverishness (chills/shivering/sweating)
- Malaise (General Unwell Feeling)

- Fatigue (Tiredness)
- Myalgia (Body Aches/Muscular Pain)
- Headache
- Nausea
- Loss of Appetite
- Elevated Oral Temperature

Pre-second dose, safety events will include all safety assessments through Day 8 post-dose 1. If the second dose occurred on Day 8, Day 8 pre-second dose safety events will include memory aid assessments and in-clinical assessments that occurred prior to dose 2.

Safety data will be summarized for the Safety Analysis Population. Pre-second vaccination, Study Groups 1, 2, 3 will be analyzed jointly as one study group as all three groups received the same vaccine at Day 1.

[Table 23](#) will provide an overview of safety events by study arm and overall. Solicited AEs will be summarized using the maximum severity over all days after each vaccination overall by vaccination and symptom (subjects with mild or higher severity grading, [Table 24](#)) and by severity (none, mild, moderate, severe) and symptom ([Table 25](#)). In both cases, the resulting number, percentage (observed rate) of subjects and associated exact (Clopper-Pearson) 95% CIs by symptom, any systemic symptom, any local symptom, and any symptom (systematic or local symptom) will be provided. In addition, solicited AEs will be tabulated by severity for each day after each study vaccination (Days 1 through Day 8) following each vaccination ([Table 26](#) and [Figure 4](#)). Subject-level solicited events will be provided as shown in [Listing 10](#) and [Listing 11](#).

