		n	%	95% CI	N	%	95% CI	n	%	95% CI	n	%	95% CI	n	%	95% CI	n	%	95% CI	n	%	95% CI
Induration (Functional grade)	None	x	x.x	x.x, x.x	x	x.x	x.x, x.x	x	x.x	x.x, x.x	x	x.x	x.x, x.x	x	x.x	x.x, x.x	x	x.x	x.x, x.x	x	x.x	x.x, x.x
	Mild	x	x.x	x.x, x.x	x	x.x	x.x, x.x	x	x.x	x.x, x.x	x	x.x	x.x, x.x	x	x.x	x.x, x.x	x	x.x	x.x, x.x	x	x.x	x.x, x.x
	Moderate	x	x.x	x.x, x.x	x	x.x	x.x, x.x	x	x.x	x.x, x.x	x	x.x	x.x, x.x	x	x.x	x.x, x.x	x	x.x	x.x, x.x	x	x.x	x.x, x.x
	Severe	x	x.x	x.x, x.x	x	x.x	x.x, x.x	x	x.x	x.x, x.x	x	x.x	x.x, x.x	x	x.x	x.x, x.x	x	x.x	x.x, x.x	x	x.x	x.x, x.x
Induration (Measurement grade)	None	x	x.x	x.x, x.x	x	x.x	x.x, x.x	x	x.x	x.x, x.x	x	x.x	x.x, x.x	x	x.x	x.x, x.x	x	x.x	x.x, x.x	x	x.x	x.x, x.x
	Mild	x	x.x	x.x, x.x	x	x.x	x.x, x.x	x	x.x	x.x, x.x	x	x.x	x.x, x.x	x	x.x	x.x, x.x	x	x.x	x.x, x.x	x	x.x	x.x, x.x
	Moderate	x	x.x	x.x, x.x	x	x.x	x.x, x.x	x	x.x	x.x, x.x	x	x.x	x.x, x.x	x	x.x	x.x, x.x	x	x.x	x.x, x.x	x	x.x	x.x, x.x
	Severe	x	x.x	x.x, x.x	x	x.x	x.x, x.x	x	x.x	x.x, x.x	x	x.x	x.x, x.x	x	x.x	x.x, x.x	x	x.x	x.x, x.x	x	x.x	x.x, x.x

N = Number of subjects in the Safety Analysis Population who received the specified dose.

Severity is the maximum severity reported over all solicited symptoms post dosing for each subject.

*: Subjects in treatment groups that received the same study product were analyzed jointly.

†: Based on Clopper-Pearson.

Table 26: Number and Percentage of Subjects Experiencing Solicited Events by Symptom, Severity, and Day (Study Arm 1, 2, and 3 (ChAD3) - Post Dose 1)

Symptom	Severity	Pre-Dose		Post-Dose		Day 1		Day 2		Day 3		Day 4		Day 5		Day 6		Day 7		Day 8	
		n	%	n	%	n	%	n	%	n	%	n	%	n	%	n	%	n	%	n	%
Any Symptom	None	x	x.x	x	x.x	x	x.x	x	x.x	x	x.x	x	x.x	x	x.x	x	x.x	x	x.x	x	x.x
	Mild	x	x.x	x	x.x	x	x.x	x	x.x	x	x.x	x	x.x	x	x.x	x	x.x	x	x.x	x	x.x
	Moderate	x	x.x	x	x.x	x	x.x	x	x.x	x	x.x	x	x.x	x	x.x	x	x.x	x	x.x	x	x.x
	Severe	x	x.x	x	x.x	x	x.x	x	x.x	x	x.x	x	x.x	x	x.x	x	x.x	x	x.x	x	x.x
	Not Reported	x	x.x	x	x.x	x	x.x	x	x.x	x	x.x	x	x.x	x	x.x	x	x.x	x	x.x	x	x.x
Systemic Symptoms																					
Any Systemic Symptom	None	x	x.x	x	x.x	x	x.x	x	x.x	x	x.x	x	x.x	x	x.x	x	x.x	x	x.x	x	x.x
	Mild	x	x.x	x	x.x	x	x.x	x	x.x	x	x.x	x	x.x	x	x.x	x	x.x	x	x.x	x	x.x
	Moderate	x	x.x	x	x.x	x	x.x	x	x.x	x	x.x	x	x.x	x	x.x	x	x.x	x	x.x	x	x.x
	Severe	x	x.x	x	x.x	x	x.x	x	x.x	x	x.x	x	x.x	x	x.x	x	x.x	x	x.x	x	x.x
	Not Reported	x	x.x	x	x.x	x	x.x	x	x.x	x	x.x	x	x.x	x	x.x	x	x.x	x	x.x	x	x.x
Elevated Oral Temperature	None	x	x.x	x	x.x	x	x.x	x	x.x	x	x.x	x	x.x	x	x.x	x	x.x	x	x.x	x	x.x

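### Tables 24 and 25 never use the pre-dose reactogenicity baseline, so a symptom carried into the Day 8 injection and persisting counts as a Post Dose 2 event

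*SAP*

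**What the plan says.** Protocol 7.3.2, for the Day 8 visit, states: "Pre-administration reactogenicity assessments will be performed prior to study vaccination to establish a baseline". Protocol 7.2 has the same step on Day 1, and Protocol 8.1 applies it to both doses: "Pre-administration reactogenicity assessments will be performed prior to each study vaccination to establish baseline".

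SAP 9.3.1 then sets the summary rule: "Solicited AEs will be summarized using the maximum severity over all days after each vaccination overall by vaccination and symptom". Table 24 counts subjects graded mild or higher. Table 25 splits them by grade, with the footnote "Severity is the maximum severity reported over all solicited symptoms post dosing for each subject". Protocol 11.4.2 prescribes the same maximum after each vaccination. Table 26, by day, has a Pre-Dose column for each symptom and grade, but its footnote also defines severity from post-dosing reports only.

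The second injection is scheduled at "Day 8 +2 (post first vaccination), Visit 06", the end of the first dose's solicited window. On symptoms still present at that visit, Protocol 5.4.3 says: "An unresolved or continuing Grade 1 or Grade 2 adverse event is permissible following the documented determination by the site principal investigator" or an appropriate sub-investigator. That determination must be that vaccination would not be unsafe and that the event would not interfere with evaluating adverse events or the immune response.

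**The concern.** A baseline is collected, but no rule says what it is for. Suppose a subject has Grade 1 fatigue after the prime. It is recorded before the Day 8 injection and is still Grade 1 at the in-clinic check 30 minutes after a placebo boost. Under the plain maximum, that subject enters the Post Dose 2 column of the placebo-boost arm as having a systemic reaction, although nothing changed.

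Solicited reactogenicity is the first-listed primary outcome (Protocol 3.2.1). With a 7-day interval and 20 subjects per arm, a few such subjects would visibly alter a boost-arm rate. A reader of Tables 24 and 25 could not tell which part of the rate was present before the injection.

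**Working it through.** **Step 1: does any rule use the pre-dose grade?** The places that could contain one are:

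- *SAP 9.3.1, Tables 24 and 25:* maximum after each dose, with no reference to the pre-dose grade.
- *SAP 9.3.1, Day 8 split:* records made before dose 2 go to dose 1. Nothing is said about a symptom that continues past dose 2.
- *SAP 9, opening paragraph:* conditions present at screening are baseline unless they worsen or become more frequent. Screening precedes dose 1, so this cannot cover a symptom first present at Day 8.
- *SAP 9.6:* a Grade 1 laboratory value at baseline is reported as an event only on reaching Grade 2 or higher. Solicited events have no equivalent rule.
- *Table 26:* shows pre-dose counts, but as marginal totals. They do not show which subjects counted after the dose were the ones with a pre-dose symptom, so Tables 24 and 25 cannot be corrected from them. Listings 10 and 11 would allow only a manual check.

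No rule uses the pre-dose grade.

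**Step 2: can a symptom run across the second injection?** Yes, at Grade 1 or 2, subject to the Protocol 5.4.3 determination. To be counted it must also persist to at least one post-dose record.

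**Step 3: which columns are affected?** Mainly Post Dose 2. The Post Either Dose columns are largely unaffected by prime carry-over, because a symptom that began within the dose 1 window is already counted there.

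**Step 4: size.** The plan states no figure that depends on this rule, so there is none to reproduce, and the documents give no carry-over rate. The following are illustrations only.

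*One arm of 20 with no new reaction after dose 2* (Clopper-Pearson 95% CI, the SAP's method). A new-or-worsened count gives 0/20 throughout, CI 0 to 16.8%.

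| Subjects with a carried-over symptom | Plain maximum | 95% CI |
|---|---|---|
| 1 | 1/20 = 5% | 0.1 to 24.9% |
| 2 | 2/20 = 10% | 1.2 to 31.7% |
| 4 | 4/20 = 20% | 5.7 to 43.7% |

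*Contrast with the placebo boost.* Let p be the true new-reaction rate and c a carry-over rate that is equal in all arms and independent of p. The tabulated rate is 1 − (1 − p)(1 − c), so the difference between two arms becomes (1 − c) times the true difference. With assumed p of 5% (placebo boost) and 40% (active boost), a true difference of 35 points:

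| Assumed c | Placebo boost | Active boost | Difference |
|---|---|---|---|
| 5% | 9.8% | 43% | 33.3 points |
| 10% | 14.5% | 46% | 31.5 points |
| 20% | 24.0% | 52% | 28.0 points |

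For scale, the 95% half-width of a difference between 40% and 5% with 20 per arm is 1.96 × √(0.40×0.60/20 + 0.05×0.95/20) = 1.96 × 0.120 ≈ 23.5 points.

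**Step 5: would a new-or-worsened count alone be right?** No. A subject with pre-dose Grade 1 fatigue that resolves, followed by a genuine Grade 1 fatigue reaction on Day 3, is dropped. In the worst case every such reaction is lost and the rate becomes p(1 − c). At c = 10% that is 36% v 4.5%, a difference of 31.5 points, the same dilution as under the plain maximum.

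**The case against.** The strongest case for leaving the tables alone has four parts.

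1. *The plain maximum is the prespecified endpoint.* Protocol 3.2.1 and 11.4.2 define it without a new-or-worsened condition, and counting every post-dose symptom is an inclusive choice for safety. This stands, and it is why the maximum should remain the main count. Neither document, however, gives that reason or says what the baseline is for.
2. *The design already deals with carry-over.* SAP 4.2 relies on the placebo boost to account for dose 1 effects lasting beyond Day 8, and no between-arm safety test is planned. This stands for contrasts, apart from the factor (1 − c). It does not help the per-arm rates and intervals, which are what Tables 24 and 25 report.
3. *Carry-over is restricted.* Protocol 5.4.3 withholds dose 2 for symptoms that could confound reactogenicity, defers it for transient symptoms or a temperature of 100.0°F or more until they have resolved or are improving, and bars it for an ongoing Grade 3 event. Dose 2 goes into the opposite deltoid (Protocol 6.2), so local residue from the prime is not at the new site. Protocol 2.3.1 reports that systemic events in previous studies mostly began within 24 hours and generally resolved within 24 hours. All of this stands and points to a small effect.
4. *Table 26 already displays pre-dose symptoms.* True, but only as marginal counts (Step 1).

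A reader might also infer that SAP 9 applies the opposite rule to unsolicited events. It does not. Its baseline statement is general and tied to screening, so it sets no Day 8 baseline for unsolicited events either.

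**Conclusion.** The point holds as a modest gap in the analysis plan. The solicited-event tables do not use a baseline that the protocol collects, and a persisting Grade 1 or 2 symptom, mainly systemic, can be counted as a Post Dose 2 event. Each such subject with no new reaction adds 1/20 = 5 points to a boost-arm rate. The likely direction is inflated per-arm rates and slightly diluted contrasts with the placebo boost, assuming that carry-over is similar across randomized arms.

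Three stronger readings are tempting, and the documents do not support them. One is that the inflation is large: no carry-over rate is given, the evidence in Protocol 2.3.1 and 5.4.3 points low, and the illustrated dilution (1.7 to 7 points off 35) is well inside the 23.5-point half-width. Another is that the rule favors one active arm: carry-over arises before the arms diverge. The last is that new-or-worsened should replace the current count: Step 5 shows that it has its own loss.

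**What to change.** In SAP 9.3.1, state that the all-reports maximum is the main count and is taken without regard to the pre-dose grade. Beside it in Tables 24 and 25, add a supplementary count, by symptom and dose, of subjects whose post-dose grade exceeds their own pre-dose grade for that symptom and dose. For the any-systemic, any-local and any-symptom rows, count a subject if at least one component symptom qualifies. Leave Table 26 unchanged.

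A footnote should say that the supplementary count misses a genuine new reaction of the same or lower grade after a pre-dose symptom has resolved, so the two counts are to be read together. If carry-over is rare they will nearly agree, and the report can show that.

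The cost is a few lines of SAP text, one derived flag from data already collected and extra columns in two tables. No study procedure changes. The rule should be fixed before the final database lock, by which time Protocol 11.4 requires the SAP to be final, so that it is not chosen after the results are seen.

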14.3.1.2 Unsolicited Adverse Events

Table 27: Number and Percentage of Subjects Experiencing Vaccine-related Unsolicited Adverse Events with 95% Confidence Intervals by MedDRA® System Organ Class and Preferred Term, and Treatment Group

MedDRA System Organ Class	MedDRA Preferred Term	Study Arm 1 ChAd3+Placebo (N=X)			Study Arm 2 ChAd3+ChAd3 (N=X)			Study Arm 3 ChAd3+MVA-BN (N=X)		
		n	%	95% CI†	n	%	95% CI†	n	%	95% CI†
Any SOC	Any PT	x	x.x	x.x – x.x	x	x.x	x.x – x.x	x	x.x	x.x – x.x
[SOC 1]	Any PT	x	x.x	x.x – x.x	x	x.x	x.x – x.x	x	x.x	x.x – x.x
	[PT 1]	x	x.x	x.x – x.x	x	x.x	x.x – x.x	x	x.x	x.x – x.x
	[PT 2]	x	x.x	x.x – x.x	x	x.x	x.x – x.x	x	x.x	x.x – x.x
[SOC 2]	Any PT	x	x.x	x.x – x.x	x	x.x	x.x – x.x	x	x.x	x.x – x.x
	[PT 1]	x	x.x	x.x – x.x	x	x.x	x.x – x.x	x	x.x	x.x – x.x
	[PT 2]	x	x.x	x.x – x.x	x	x.x	x.x – x.x	x	x.x	x.x – x.x

Note: N = number of subjects in the Safety Analysis Population.

This table presents number and percentage of subjects. A subject is only counted once per PT.

†: Based on Clopper-Pearson.

Table 28: Number and Percentage of Subjects Experiencing Any Unsolicited Adverse Events with 95% Confidence Intervals by MedDRA® System Organ Class and Preferred Term, and Treatment Group

MedDRA System Organ Class	MedDRA Preferred Term	Study Arm 1 ChAd3+Placebo (N=X)			Study Arm 2 ChAd3+ChAd3 (N=X)			Study Arm 3 ChAd3+MVA-BN (N=X)		
		n	%	95% CI†	n	%	95% CI†	n	%	95% CI†
Any SOC	Any PT	x	x.x	x.x – x.x	x	x.x	x.x – x.x	x	x.x	x.x – x.x
[SOC 1]	Any PT	x	x.x	x.x – x.x	x	x.x	x.x – x.x	x	x.x	x.x – x.x
	[PT 1]	x	x.x	x.x – x.x	x	x.x	x.x – x.x	x	x.x	x.x – x.x
	[PT 2]	x	x.x	x.x – x.x	x	x.x	x.x – x.x	x	x.x	x.x – x.x
[SOC 2]	Any PT	x	x.x	x.x – x.x	x	x.x	x.x – x.x	x	x.x	x.x – x.x
	[PT 1]	x	x.x	x.x – x.x	x	x.x	x.x – x.x	x	x.x	x.x – x.x
	[PT 2]	x	x.x	x.x – x.x	x	x.x	x.x – x.x	x	x.x	x.x – x.x

Note: N = number of subjects in the Safety Analysis Population.

This table presents number and percentage of subjects. A subject is only counted once per PT.

†: Based on Clopper-Pearson.

Table 29: Unsolicited Adverse Events by MedDRA System Organ Class and Preferred Term, Maximum Severity, Relationship, and Treatment Group

MedDRA System Organ Class	Preferred Term	Severity	Study Arm 1 ChAd3+Placebo (N=X)						Study Arm 2 ChAd3+ChAd3 (N=X)						Study Arm 3 ChAd3+MVA-BN (N=X)					
			Related		Not Related		Total		Related		Not Related		Total		Related		Not Related		Total	
			n	%	n	%	n	%	n	%	n	%	n	%	n	%	n	%	n	%
Any SOC	Any PT	Any Severity	x	x.x	x	x.x	x	x.x	x	x.x	x	x.x	x	x.x	x	x.x	x	x.x	x	x.x
		Mild	x	x.x	x	x.x	x	x.x	x	x.x	x	x.x	x	x.x	x	x.x	x	x.x	x	x.x
		Moderate	x	x.x	x	x.x	x	x.x	x	x.x	x	x.x	x	x.x	x	x.x	x	x.x	x	x.x
		Severe	x	x.x	x	x.x	x	x.x	x	x.x	x	x.x	x	x.x	x	x.x	x	x.x	x	x.x
SOC 1	PT 1	Any Severity	x	x.x	x	x.x	x	x.x	x	x.x	x	x.x	x	x.x	x	x.x	x	x.x	x	x.x
		Mild	x	x.x	x	x.x	x	x.x	x	x.x	x	x.x	x	x.x	x	x.x	x	x.x	x	x.x
		Moderate	x	x.x	x	x.x	x	x.x	x	x.x	x	x.x	x	x.x	x	x.x	x	x.x	x	x.x
		Severe	x	x.x	x	x.x	x	x.x	x	x.x	x	x.x	x	x.x	x	x.x	x	x.x	x	x.x
	PT 2	Any Severity	x	x.x	x	x.x	x	x.x	x	x.x	x	x.x	x	x.x	x	x.x	x	x.x	x	x.x
		Mild	x	x.x	x	x.x	x	x.x	x	x.x	x	x.x	x	x.x	x	x.x	x	x.x	x	x.x
		Moderate	x	x.x	x	x.x	x	x.x	x	x.x	x	x.x	x	x.x	x	x.x	x	x.x	x	x.x
		Severe	x	x.x	x	x.x	x	x.x	x	x.x	x	x.x	x	x.x	x	x.x	x	x.x	x	x.x

N = Number of subjects in the Safety Population. For severity, a subject is counted once per preferred term and is summarized according to their highest severity. For vaccine-relatedness, a subject is only counted once per preferred term and is summarized according to their closest relationship.

14.3.2 Listing of Deaths, Other Serious and Significant Adverse Events**Table 30: Listing of Serious Adverse Events**

Adverse Event	Associated with Dose #	# of Days Post Associated Dose (Duration)	# of Days Post Dose the Event Became Serious	Reason Reported as an SAE	Severity	Relationship to Study Treatment	If Not Related, Alternative Etiology	Action Taken with Study Treatment	Subject Discontinued Due to AE	Outcome	MedDRA System Organ Class	MedDRA Preferred Term
Subject ID: , Treatment Group: , AE Number:												
Comments:												
Subject ID: , Treatment Group: , AE Number:												
Comments:												

Table 31: Listing of Vaccine-Related Medically Attended Adverse Events

Adverse Event	Associated with Dose No.	No. of Days Post Associated Dose (Duration)	Severity	Relationship to Study Treatment	If Not Related, Alternative Etiology	Action Taken with Study Treatment	Subject Discontinued Due to AE	Outcome	MedDRA System Organ Class	MedDRA Preferred Term
Subject ID: Treatment Group: AE Number:										
Comments:										
Subject ID: Treatment Group: AE Number:										
Comments:										

Table 32: Listing of Non-Serious, Unsolicited, Moderate or Severe Adverse Events

Adverse Event	Associated with Dose #	# of Days Post Associated Dose (Duration)	Severity	Relationship to Study Treatment	If Not Related, Alternative Etiology	Action Taken with Study Treatment	Subject Discontinued Due to AE	Outcome	MedDRA System Organ Class	MedDRA Preferred Term
Subject ID: , Treatment Group: , AE Number:										
Comments:										
Subject ID: , Treatment Group: , AE Number:										
Comments:										

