11.4.2. Safety Data

Safety data will be summarized for the Safety Analysis Population. Pre-second vaccination, Study Groups 1, 2, 3 will be analyzed jointly as one study group as all three groups received the same vaccine at Day 1.

Solicited AEs will be summarized by severity for each day after each study vaccination (Days 1 through 7 days post-vaccination) and as the maximum severity over all days after each vaccination. The maximum severity of local and systemic reactions will be determined for each subject and summarized by study group following each vaccination (as well as post any vaccination) and the resulting number, percentage (observed rate) of subjects and associated exact 95% confidence interval (CI) will be summarized by severity grade (none, mild, moderate, severe) and symptom. Summaries will also be provided for any systemic symptoms, for any local symptoms, and for any systematic or local symptoms.

Vaccine-related unsolicited AEs from the first study vaccination through 28 days post second vaccination will be coded by Medical Dictionary for Regulatory Activities (MedDRA®) for preferred term and system organ class (SOC). These AEs will be summarized as number and percentage of subjects reporting at least one event in each MedDRA® preferred term and SOC, cross tabulated by severity grade (none, mild, moderate, severe). Additionally, the number, percentage (observed rate) and exact two-sided 95% CI for subjects reporting a related unsolicited AE overall, by SOC, and by preferred term will be summarized by study group.

Clinical safety laboratory AEs from the time of first study vaccination through approximately 28 days after the second vaccination will be summarized by severity grade (none, mild, moderate, severe) for each laboratory visit. In addition, the maximum severity over all post-vaccination visits will be summarized by study visit and by severity grade (none, mild, moderate, severe) using percentages and exact two-sided 95% CIs.

The number of SAEs and vaccine-related Medically Attended Adverse Events (MAAEs) through 6 months post first vaccination will be reported by detailed listings showing the event description, preferred term and SOC, relevant dates (study vaccinations and AEs), severity, vaccine-relatedness, and outcome for each event.

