3.2. Study Outcome Measures

3.2.1. Primary

- Frequency and severity of solicited local and systemic reactogenicity from the time of study vaccine administration through 7 days post-vaccination.
- Frequency and severity of vaccine-related unsolicited adverse events (AEs) from the first study vaccination through 28 days post second vaccination.
- Frequency and severity of clinical safety laboratory AEs from the time of first study vaccination through approximately 28 days after the second vaccination.
- Frequency of Serious Adverse Events (SAEs) and vaccine-related Medically Attended Adverse Events (MAAEs) through 6 months post first vaccination.

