6. GENERAL STATISTICAL CONSIDERATIONS

6.1. General Principles

Continuous variables will be summarized using descriptive statistics: n (non-missing sample size), mean, standard deviation, median, interquartile range, min, and max) unless otherwise specified. The frequency and percentages (based on the analysis population size) of observed levels will be reported for all categorical measures. In general, all data will be listed, sorted by study arm (1-3), subject, and when appropriate, by study visit number within subject. Unless otherwise specified, study arm labels shown in tables and figures will include the total population size relevant to the particular analysis. As subjects in all study arms will receive the same study product (ChAd3-EBO-Z) for the first vaccination (Table 1), results prior to the second vaccination (up to and including Day 8) will be presented jointly as “Study Arms 1, 2, and 3 (ChAd3)”. Post-second vaccination results will be presented separately for each of the three study arms.

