9.3.2. Unsolicited Adverse Events

Vaccine-related unsolicited AEs from the first study vaccination through 28 days post second vaccination will be coded by Medical Dictionary for Regulatory Activities (MedDRA®) for preferred term and system organ class (SOC) ([Table 27](#)). These AEs will be summarized as number and percentage of subjects reporting at least one event in each MedDRA® preferred term and SOC, cross tabulated by severity grade (none, mild, moderate, severe). Corresponding results for all unsolicited AEs will be presented by study arm as shown in [Table 28](#). A categorization by severity and vaccine-relatedness by study arm will be provided as provided in [Table 29](#). Subject-level unsolicited adverse events will be provided as shown in [Listing 10](#).

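### Unsolicited AEs (Tables 27–29) are tabulated only cumulatively by arm, without the pooled pre-boost and by-arm post-boost view the SAP sets as its general rule; Table 38 splits pre-boost Day 8 vital signs by arm

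*SAP*

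**What the plan says.** **General rule.** SAP 6.1 (General Principles) states that "results prior to the second vaccination (up to and including Day 8) will be presented jointly", because all arms receive the same first product, and that "Post-second vaccination results will be presented separately for each of the three study arms". Protocol 11.4.2 (Safety Data) opens with the same pooling rule for safety data: "Pre-second vaccination, Study Groups 1, 2, 3 will be analyzed jointly as one study group". SAP 9.3.1 repeats it. None of these places exempts unsolicited events.

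**Unsolicited AEs.** The primary outcome in SAP 3.2.1 covers "vaccine-related unsolicited adverse events (AEs) from the first study vaccination through 28 days post second vaccination". SAP 9.3.2 uses the same single window: "Vaccine-related unsolicited AEs from the first study vaccination through 28 days post second vaccination will be coded". The shell for it in SAP Appendix 1 is Table 27, whose title begins "Number and Percentage of Subjects Experiencing Vaccine-related Unsolicited Adverse Events with 95% Confidence Intervals". Protocol 11.4.2 asks that the number, percentage and exact interval "for subjects reporting a related unsolicited AE overall, by SOC, and by preferred term will be summarized by study group". For solicited events the same protocol section goes further and wants maximum severity "summarized by study group following each vaccination (as well as post any vaccination".

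**Vital signs.** SAP 9.7 tabulates vital signs by study day for each treatment group separately. Protocol 8.1 says that at every vaccination visit they are taken before the injection.

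**The concern.** The three arms differ only in the Day 8 injection. The first dose is therefore best described from all subjects together, and the boost from the period after it, arm by arm. SAP 6.1 makes this its presentation rule, and the solicited and laboratory tables apply it. The unsolicited tables put both periods into one count per arm, so a reader of Table 27 cannot tell whether an arm's related events came before or after the boost. Vaccine-related unsolicited AEs are one of the primary outcomes, so their summary tables should give the same view as the others.

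Table 38 has the reverse problem. It shows by arm a measurement taken when the arms had been treated identically, so any difference in that row cannot be due to the boost.

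**Working it through.** **Shells set side by side (SAP Appendix 1)**

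| Display | Pre-boost, arms pooled | Post-boost, by arm | Both doses, by arm |
|---|---|---|---|
| Tables 24–25, solicited | yes | yes | yes |
| Table 26 and its repeats, solicited by day | yes | yes | no |
| Tables 35–37, laboratory | Day 8 row pooled | yes | maximum post baseline |
| Tables 27–29, unsolicited | no | no | yes |
| Table 23, overview | no | no | yes, plus all subjects |
| Table 38, vital signs | baseline pooled; Day 8 split by arm | no later visit shown | no |

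Tables 27–29 use the whole safety population as N, and no note asks for a repeat by dose. Figures 5–12 are titled as post any vaccination. The plan states no figure on this point, so there is none to reproduce.

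**Length of the pre-boost period.** The boost visit is Day 8 with a window of +2 days (protocol 7.3.2), so the pre-boost period is 7 to 9 days. The outcome window closes 28 days after the second dose.
- Boost on Day 8: 7/(7 + 28) = 7/35 = 20.0% of the window.
- Boost on Day 10: 9/(9 + 28) = 9/37 = 24.3% of the window.

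**Precision gained by pooling.** Design numbers are 20 per arm and 60 in total (SAP Table 1). For 0 of n, the exact upper 95% limit is 1 − 0.025^(1/n).
- 0/60: 5.96%, or 6.0%.
- 0/20: 16.84%, or 16.8%.
- 1/60: Clopper-Pearson interval 0.04% to 8.94%.

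If Table 23 shows no related unsolicited event over both doses, 0/60 before the boost follows from it. Otherwise the pooled pre-boost count cannot be read from any summary table.

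**Effect on reading the boost.** All event rates here are assumptions, because the documents give none. Let p1 be the pre-boost risk and b the post-boost risk, taken as independent. The cumulative risk is 1 − (1 − p1)(1 − b). Take b = 5% in one arm and 25% in another, a true difference of 20 points. The SD of an arm difference with 20 per arm is √{[pA(1 − pA) + pB(1 − pB)]/20}.

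| Assumed p1 | Cumulative risks | Difference (points) | SD (points) |
|---|---|---|---|
| Post-boost only | 5% v 25% | 20.0 | 10.84 |
| 2% | 6.9% v 26.5% | 19.6 | 11.38 |
| 5% | 9.75% v 28.75% | 19.0 | 12.10 |
| 10% | 14.5% v 32.5% | 18.0 | 13.10 |

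The cumulative display costs 0.4 to 2.0 points of difference and adds 0.54 to 2.26 points of SD.

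**The case against.** The strongest reply is that no analysis the plan asks for is missing. The text specific to this outcome defines one window and asks for a summary by study group; only solicited events are requested after each vaccination. SAP 9 expects some results not to be split, since its denominator is the safety population unless results are shown by dose. SAP 4.2 explains that the placebo-boost arm allows for first-dose effects lasting beyond Day 8. Because the first dose is the same in all randomised arms, the cumulative comparison between arms is valid. Most of this stands, and it is why the existing columns should be kept. It does not remove the general pooling rule, which appears in the same protocol section without exemption and which the SAP applies beyond solicited events. A request for a cumulative summary does not rule out the period view.

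A second reply also stands in full: Listing 12 covers every unsolicited event, with severity, relationship, associated dose and days since that dose. With about 60 subjects, that one listing is enough to rebuild the split.

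On Table 38, SAP 9.7 could be read as a specific exception to SAP 6.1. The table's own pooled baseline row, its footnote on joint analysis, and the pooled Day 8 rows of Tables 35–37 all weaken that reading.

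**Conclusion.** There is a minor gap between the table shells and the plan's own presentation rule, together with one direct inconsistency between SAP 9.7 and SAP 6.1. The shell comparison rests on the text alone. The size of the effect on a boost comparison rests on assumed rates and independence of the two periods, and is modest throughout the range shown. No between-arm safety test is planned, and the study tests no formal hypothesis, so no error rate or sample size is affected.

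Three stronger readings are not supported:
- **That the primary outcome is missing or wrongly reported.** Table 27 delivers it over the window that SAP 3.2.1 defines.
- **That an event on Day 9 or 10, before a late boost, belongs to neither period.** SAP 6.1 turns on whether the result precedes the second vaccination. Day 8 is also the name of the boost visit, which has a +2 day window. SAP 9.3.1's cut at Day 8 sits in the solicited-events section.
- **That a pooled pre-boost column would give the full first-dose rate.** It covers 7 to 9 days; later first-dose events fall in the post-dose-2 columns of every arm.

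**What to change.** **Unsolicited AEs.** Keep the cumulative by-arm columns. Add to Table 27, and to the related columns of Table 29:
- one pooled pre-boost column, with N = all who received dose 1, labelled as a rate over roughly 7 to 9 days;
- three post-dose-2 columns by arm, with N = those who received dose 2, in line with the by-dose denominator in SAP 9.

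The same addition to Table 28 is optional. Assign each event by its onset relative to the subject's actual second vaccination, not to nominal Day 8. State in SAP 9.3.2 how an onset on the day of the boost is assigned and how subjects who never receive dose 2 are counted.

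**Vital signs.** Show the Day 8 row of Table 38 pooled over arms, and amend SAP 9.7 to match SAP 6.1.

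**Cost.** A few sentences of SAP text, wider tables and some programming. No new data are needed: protocol 9.2.1 lists date of onset among the items collected for unsolicited AEs, and Listing 12 already plans an associated-dose column. Associated dose is not in the protocol 9.2.1 list, so it may have to be derived from the dates.
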